6. STATISTICAL ANALYSIS PLAN (SAP)

Primary Outcomes

Primary outcomes are feasibility, acceptability, and appropriateness of the PEERNaija app. These will be assessed through Weiner’s validated feasibility of intervention measure (FIM), acceptability of intervention measure (AIM), and appropriateness of intervention measure (IAM) at six months. The FIM, AIM, and IAM surveys each contain four statements and participants are asked to rate their level of agreement to each statement on a Likert scale of 1-5, with 1 being “completely disagree” and 5 being “completely agree.”

Participants will answer study team-generated questions assessing the acceptability and appropriateness of individual app features and the app overall via feedback questionnaires administered at 12 and 24 weeks.

Secondary Outcomes

Secondary outcome is preliminary efficacy on viral load. This will be assessed by comparing change in HIV viral load (from baseline to 24 weeks), and self-reported adherence from baseline to 12 weeks, and baseline to 24 weeks. ART adherence will also be assessed at baseline and six months using a visual analogue scale where participants indicated the percentage of prescribed ART doses taken over the past 30 days.

Additional covariates are assessed at baseline, and include depression, digital health care literacy, self-reported ART self-efficacy and adherence, HIV stigma, social support, and alcohol and substance use. Depression was assessed through the Patient Health Questionnaire, version 9 (PHQ-9). The PHQ-9 contains 9 items on the frequency of depressive symptoms in the past two weeks; total scores range from 0-27 and higher scores indicate a higher severity of depressive symptoms. Digital health care literacy will be assessed through the Digital Health Care literacy scale. The Digital Health Care Literacy Scale contains 3 items on comfort and ability with using technology; total scores range from 0-12 and higher scores indicate higher literacy. ART self-efficacy will be assessed through the HIV Medication Taking Self-efficacy Scale (MT SES). The MT SES contains 16 items on confidence in managing HIV treatment; total scores range from 1-10 and higher scores indicate higher self-efficacy. HIV stigma was assessed through Berger's HIV Stigma Scale. Berger's stigma scale contains 40 items on perceived stigma, fears related to disclosure, negative self-image due to HIV status, and perceived community stigma; total scores range from 40-160 and higher scores indicate higher HIV stigma. Social support will be assessed through the Social Provisions Scale. The Social Provisions Scale contains 24 items on support individuals receive from their social networks; total scores range from 24-96 and higher scores indicate higher social provisions. Alcohol and substance use was assessed through the CRAFFT screening tool. CRAFFT contains 3 items on substance use in the past twelve months; total scores range from 0-3 and higher scores indicate a need for further assessment.

Analysis Plan

Descriptive analyses will be performed to describe the distributional statistics of interested variables, including demographic variables, clinical, and psychosocial characteristics, at baseline and during follow-up assessments. For continuous variables, the mean and standard error will be reported; for categorical variables, frequencies and percentages will be presented.

Comparisons of primary outcomes (feasibility, acceptability and appropriateness) will be performed by comparing mean FIM, AIM, and IAM scores respectively between PEERNaija and PEERNaija+ at 24 weeks using two-sample t-tests. These constructs will additionally be addressed by comparing questions from feedback questionnaires, specifically assessing percentage of reminders received and whether or not reminders or chat messaged were intrusive, whether it was helpful to see their peers' adherence scores, whether they would use the app after the study, and whether they would recommend the app to a peer.

Comparisons between secondary outcomes (viral load and self-reported adherence) will be assessed by conducting a pre-post comparison of adherence measures at baseline, 12, and at 24 weeks, and pre-post comparison of viral load measures at baseline and 24 weeks in the two study groups (*PEERNaija* and *PEERNaija+*), using paired tests (e.g., paired t-tests, signed rank tests, or McNemar's tests, as appropriate), with a significance level set at $p \leq .05$ (2-tailed test). Further, self-reported preliminary efficacy will be assessed via response to feedback questionnaire question asking whether the app helped them to miss fewer medication doses and responses across study groups using Chi-square tests.

To further explore associations between outcomes and variables of interest, univariate regression analyses will be performed. Linear regression will be applied to continuous outcomes, including the primary outcomes (FIM, AIM, and IAM score) and self-reported adherence; while logistic regression will be used for binary outcomes such as viral suppression status at the study end.

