3. STUDY OBJECTIVE AND HYPOTHESIS

SPECIFIC AIM: To establish the feasibility, acceptability, and preliminary efficacy of *PEERNaija*, an mHealth intervention designed to harness peer influence as an incentive to promote medication adherence among a pilot cohort of 50 AYA living with HIV in Nigeria.

[figure not shown]
Hypothesis: *PEERNaija* will be feasible, acceptable, and show preliminary efficacy in improving ART adherence.

4. METHODS (TO INCLUDE STUDY DESIGN, DETERMINATION OF SAMPLE SIZE, EXCLUSION/INCLUSION CRITERIA, ANALYSES OF DATA, ETC.)

Eligibility and Enrollment: We will conduct a prospective pilot study of the *PEERNaija* application for 50 AYA living with HIV in Nigeria. Patients will be recruited from the APIN HIV clinic and will be eligible for this study if they 1) own a smartphone (on which they are willing to download *PEERNaija*), 2) are 14-29 years of age, 3) are on ART, and 4) demonstrate the ability read simple text language in English. Patients will provide written informed consent for study participation.

Intervention Description: All participants will receive daily medication reminders, access to the virtual support group, and other key features identified in Aim 1. In addition, participants will be randomized to receive the social incentive (n=25) or the social plus financial incentive (n=25), *PEER+* and be followed for 24 weeks.

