Study Outcomes: The outcomes of interest for this study are feasibility, acceptability, adoption, and preliminary efficacy, and will be measured at 24 weeks. Preliminary efficacy will be assessed by comparing change in HIV viral load, and adherence from baseline to 12 weeks, and baseline to 24 weeks. We hypothesize that the *PEERNaija* mHealth application will be feasible and acceptable, and show preliminary efficacy in improving HIV virologic control. The study outcomes will be assessed through a combination of a) questionnaires administered to study participants b) clinical measures or correlates of adherence measured at baseline and at each study visit, and (c) analysis of usage data collected during routine use of the application. Chat feature use will be measured by monitoring the monthly frequency of posts per participant in addition to the thematic content.

Data analysis: Study feasibility and acceptability will be measured by analyzing the content of the feedback surveys at each study visit, and the FGDs at study end. Adoption will be assessed by analyzing usage data. Preliminary efficacy will be assessed by conducting a pre–post comparison of adherence measures, HIV viral load, and adoption measures at baseline, 12, and at 24 weeks in the two study groups (*PEER* and *PEER+*). De-identified chatroom the chat posts will be downloaded from the coordinator application, and reviewed from weeks 0-12 and 12-24.

5. ETHICAL CONSIDERATION. CONSENT DOCUMENTATION (TRANSLATION TO LOCAL LANGUAGES WHERE APPLICABLE) AND PATIENT INFORMATION LEAFLET (WHERE APPLICABLE)

A. Risks to the Subjects

A.1. Human Subjects Involvement and Characteristics. This study will involve several participants, namely:

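### The hypothesis asks whether the app is feasible and acceptable, but the test named for the primary scores only compares two arms that both use it, and no criterion is set for the level itself

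*Combined protocol and SAP*

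**What the plan says.** Section 3 gives the aim as "To establish the feasibility, acceptability, and preliminary efficacy of" the app in a pilot cohort of 50. The hypothesis is that the app "will be feasible, acceptable, and show preliminary efficacy in improving ART adherence". Study Outcomes in section 4 repeats it: the "mHealth application will be feasible and acceptable, and show preliminary efficacy in improving HIV virologic control". None of these statements contrasts the two arms on feasibility or acceptability.

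Section 4, Intervention Description, gives the app to everyone: "All participants will receive daily medication reminders, access to the virtual support group" and other key features. Randomisation, 25 to each arm, is between the social incentive alone and the social plus financial incentive.

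Section 6 states: "Primary outcomes are feasibility, acceptability, and appropriateness of the PEERNaija app". FIM, AIM and IAM each have four items rated 1 to 5. The Analysis Plan then specifies "comparing mean FIM, AIM, and IAM scores respectively between PEERNaija and PEERNaija+ at 24 weeks using two-sample t-tests".

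Other parts of the plan bear on the same constructs:

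- Section 4, Data analysis: "Study feasibility and acceptability will be measured by analyzing the content of the feedback surveys at each study visit", plus focus groups at study end. Usage data are analysed for adoption.
- Section 6, Analysis Plan, descriptive paragraph: analyses will "describe the distributional statistics of interested variables, including demographic variables, clinical, and psychosocial characteristics, at baseline and during follow-up assessments", with mean and standard error for continuous variables.
- Section 6, Analysis Plan: feedback-questionnaire items are also compared, and exploratory univariate linear regressions are run on the three scores.

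**The concern.** A test between two groups that both use the app cannot show whether the app is acceptable. It answers a different question, namely whether the added financial incentive shifts the ratings. A significant difference would be compatible with both arms disliking the app, and a non-significant one with both liking or both disliking it.

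Section 7 presents the project as the basis for a larger trial. Whether the app is feasible and acceptable enough to take forward depends on the level of the scores. With no criterion fixed beforehand, a middling mean could be called success or failure once it is known. A non-significant arm difference might also be taken as support for acceptability, although with 25 per arm it is the likely result unless the arms differ widely.

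**Working it through.** **No figure to reproduce.** The documents give no SD, target, margin or power statement for FIM, AIM or IAM, and no calculation behind the 50. The mismatch is one of logic; the arithmetic below shows what each analysis could deliver.

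**Inputs from the documents**
- 25 per arm, 50 in total (section 4).
- Four items per measure, each rated 1 to 5 (section 6).
- Two-sided 5% level. The SAP states this only for the secondary paired tests; it is assumed here for the primary t-tests.

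**Assumptions**
- Each score is the mean of its four items, so its midpoint is 3. The SAP does not say whether items are averaged or summed.
- SD of 0.5, 0.75 or 1.0 points.
- 50 participants scored, or 40 (a 20% loss).

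**Step 1: does the named test respond to the level?** The statistic is t = (difference between arm means) / (SD × √(2/n)), with n per arm. The overall level does not appear in it. For a difference of 0.1 and 25 per arm, √(2/25) = 0.283, so:
- SD 0.5: t = 0.1/0.141 = 0.707, p = 0.48
- SD 0.75: t = 0.1/0.212 = 0.471, p = 0.64
- SD 1.0: t = 0.1/0.283 = 0.354, p = 0.73

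These hold at any overall level. As a check, 20,000 simulated trials were run at each of three levels, with equal arm means, SD 0.75 and scores limited to 1–5. The test rejected in 5.1%, 5.1% and 4.9% of trials when both arms had a mean of 2.0, 3.0 and 4.3.

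**Step 2: precision of each quantity.** The 95% half-width is t(n−1) × SD/√n for one mean and t(2n−2) × SD × √(2/n) for the arm difference, with n per arm.

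| Quantity | SD 0.5 | SD 0.75 | SD 1.0 |
|---|---|---|---|
| Overall mean, 50 scored | 0.142 | 0.213 | 0.284 |
| Overall mean, 40 scored | 0.160 | 0.240 | 0.320 |
| One-arm mean, 25 scored | 0.206 | 0.310 | 0.413 |
| Arm difference, 25 per arm | 0.284 | 0.427 | 0.569 |
| Arm difference, 20 per arm | 0.320 | 0.480 | 0.640 |

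The interval for the arm difference is twice as wide as the interval for the overall mean from the same participants.

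**Step 3: power of the named test.** By the noncentral t distribution with 25 per arm, power is 11%, 41% and 79% for true differences of 0.2, 0.5 and 0.8 SD. Power of 80% needs 0.809 SD, which is 0.40, 0.61 or 0.81 points for the three SDs. With 20 per arm it needs 0.91 SD.

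**Step 4: what an absolute criterion would look like.** As an illustration only, take a lower 95% bound above the midpoint of 3. The observed overall mean would then have to exceed 3 plus the half-width: 3.14 to 3.28 with 50 scored, or 3.16 to 3.32 with 40.

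**Step 5: why the criterion must come first.** With 50 scored and SD 1.0, an observed mean of 3.3 gives 3.3 ± 0.284, or 3.02 to 3.58. That interval clears the midpoint but leaves the mean well short of 4. Without a stated benchmark, either reading is open.

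**The case against.** The strongest reply is that the SAP never calls the t-test the primary analysis. It describes how the arms are compared, while the level is covered elsewhere. The list in the descriptive paragraph is not exhaustive, the SAP treats the three scores as continuous, and a mean with its standard error yields a confidence interval. Feedback items, focus groups and usage data add further absolute evidence. The arm contrast is a legitimate pilot question, because the trial randomises the financial incentive. A formal threshold may also be more than a 50-person pilot needs.

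Much of this stands. The level will probably be visible, and the arm comparison is worth keeping. Two narrower points are also fair: the stated hypotheses name feasibility and acceptability but not appropriateness, so the mismatch applies most directly to FIM and AIM; and section 7 sets out no formal go/no-go decision.

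These points do not close the gap. The descriptive paragraph does not name FIM, AIM or IAM. The feedback items are again to be compared, with no success proportion given, and the regressions explore associations. Reporting a mean is not a rule for judging it, and the visible text contains no target mean, target proportion, interval rule or progression criterion. A pilot meant to support a larger trial has particular need of one.

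**Conclusion.** The concern holds and should be fixed. No result of the test named for the primary scores can support or refute the hypothesis that the app is feasible and acceptable, and no visible text says how the level of those scores will be judged. This follows from the design and does not depend on any assumed number.

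The size figures do rest on assumptions: SDs of 0.5 to 1.0, averaged items, 40 or 50 scored, and a two-sided 5% level. On that basis the arm contrast is estimated half as precisely as the overall mean, and with 25 per arm it reaches 80% power only for differences of about 0.4 to 0.8 points. The data to be collected remain fully usable for the right analysis.

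**What to change.** In the Analysis Plan of section 6:

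1. Make the primary analysis the mean FIM, AIM and IAM at 24 weeks, each with a 95% confidence interval, over all participants and by arm.
2. State, before analysis, the benchmark that counts as feasible, acceptable and appropriate. A lower 95% bound above the scale midpoint is one possible form; the documents give no basis for a particular value, so the sponsor must choose and justify it.
3. Say whether each score is the mean or the sum of its four items, so that the benchmark is unambiguous.
4. Name the three scores in the descriptive paragraph.
5. Keep the between-arm comparison as secondary, reported as a difference with its 95% confidence interval, and state that a non-significant difference is not evidence of acceptability.

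The cost is SAP wording only, with the same participants and data. The downside is that the team commits to a benchmark it might miss.

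### The between-arm comparison of FIM, AIM and IAM is valid but unadjusted; pre-specifying one baseline covariate, digital health literacy, is a cheap optional gain in precision

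*Combined protocol and SAP*

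**What the plan says.** Section 4 (Methods, Intervention Description) has participants "randomized to receive the social incentive (n=25) or the social plus financial incentive (n=25"). It describes no stratification.

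Section 6 (SAP, Primary Outcomes) defines the three scores: "The FIM, AIM, and IAM surveys each contain four statements", each rated from 1 to 5. They are taken once, as in "appropriateness of intervention measure (IAM) at six months", and no baseline value is described.

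Section 6 then lists the covariates: "Additional covariates are assessed at baseline, and include depression, digital health care literacy", followed by self-efficacy, stigma, social support and substance use. On the literacy measure it says "The Digital Health Care Literacy Scale contains 3 items on comfort and ability with using technology", with a total from 0 to 12.

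Under Analysis Plan, the arm comparison is made by "comparing mean FIM, AIM, and IAM scores respectively between PEERNaija and PEERNaija+ at 24 weeks using two-sample t-tests", with no covariate. Regression appears separately: "To further explore associations between outcomes and variables of interest, univariate regression analyses will be performed". It covers the primary scores: "Linear regression will be applied to continuous outcomes, including the primary outcomes (FIM, AIM, and IAM score) and self-reported adherence". These are one-predictor models, so they do not adjust the arm contrast.

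**The concern.** The scores are ratings of a smartphone app, so how comfortable a participant already is with technology may influence them. There is no baseline score to adjust for, which leaves a variable such as digital literacy as the natural candidate. The plan collects it but leaves it out of the randomised comparison.

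Two things follow if literacy and the ratings are correlated. The interval for the arm difference is somewhat wider than it need be. And with 25 per arm, one allocation can by chance put the more technology-able participants in one arm, so that part of the observed difference reflects literacy and not the lottery. Section 7 says the pilot will be the basis for a larger trial, so a difference between arms may be carried forward as an effect of the financial incentive.

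There is also a question of timing. Several covariates are listed and the variables for the exploratory regressions are not named. If an imbalance is noticed later, any adjustment would be chosen after the fact.

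**Working it through.** The documents give no power, target difference, SD or sample-size derivation for these scores, so there is no stated figure to reproduce. Results are in SD units of the score.

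**Inputs**
- n = 25 per arm, N = 50 (Section 4).
- Two-sided 5% level. The SAP states it in its sentence on the secondary outcomes; it is assumed here for the primary t-tests.
- Correlation r between baseline literacy and the score: not in the documents. Assumed range 0 to 0.5.
- Complete data and normal variables: assumptions.

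**Step 1. Planned t-test.** The 95% CI half-width is t(0.975, 48 df) × √(2/25) = 2.0106 × 0.2828 = 0.569 SD.

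**Step 2. Linear model with arm and literacy.** The variance is multiplied by (1 − r²) × (1 + 1/(N − 4)). The second factor, 1 + 1/46 = 1.0217, is the expected price of chance imbalance. The half-width is t(0.975, 47 df) × 0.2828 × √[(1 − r²) × 1.0217], with t = 2.0117.

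| Assumed r | Variance factor | Half-width (SD) | Change from 0.569 |
|---|---|---|---|
| 0 | 1.02 | 0.575 | +1.1% |
| 0.3 | 0.93 | 0.549 | −3.5% |
| 0.4 | 0.86 | 0.527 | −7.3% |
| 0.5 | 0.77 | 0.498 | −12.4% |

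Setting the two half-widths equal gives break-even at |r| of about 0.15. Simulation agrees: mean half-width is 0.566 SD unadjusted, against 0.572, 0.546, 0.524 and 0.496 SD adjusted at r = 0, 0.3, 0.4 and 0.5.

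**Step 3. Chance imbalance.** The difference in mean literacy between arms has SD √(2/25) = 0.28 covariate SD.
- P(imbalance above 0.3 SD) = 2 × [1 − Φ(0.3/0.2828)] = 0.29.
- P(imbalance above 0.5 SD) = 2 × [1 − Φ(0.5/0.2828)] = 0.08.

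An imbalance of 0.5 SD shifts the unadjusted difference by r × 0.5, which is 0.15 SD at r = 0.3 and 0.25 SD at r = 0.5.

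**Step 4. Error rates of the planned t-test (simulation).** Over all randomisations the type I error is about 5% at every r, and the mean estimate is unbiased. Among only the roughly 8% of allocations with imbalance above 0.5 SD, it is about 9%, 12% and 16% at r = 0.3, 0.4 and 0.5, against about 5% for the adjusted model. The remaining 92% must then run slightly below 5%. At r = 0.5, for example, (5 − 0.08 × 16)/0.92 = 4.0%.

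**Step 5. What it does for power.** The difference detectable with 80% power is 0.81 SD unadjusted. Adjusted, it is 0.82, 0.78, 0.75 and 0.71 SD at r = 0, 0.3, 0.4 and 0.5.

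**The case against.** The strongest reply is that nothing here is wrong. In a randomised comparison the t-test's standard error already allows for chance imbalance. A reader might infer from the 9% to 16% rates that the planned test is anti-conservative, or that its estimate is biased. Neither follows: those rates apply only to the worst 8% of allocations and are offset in the rest. This part of the objection stands in full.

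A reader might also infer that precision is certainly being lost, or that the SAP itself expects literacy to predict the scores. The documents support neither. Literacy is listed as a covariate, no correlation is given, and the regressions are described as exploratory without naming it. Below |r| of about 0.15 the adjustment costs a little precision. Section 4 requires smartphone ownership, willingness to download the app and ability to read English, which may narrow the range of technology ability and weaken the correlation.

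The aim in Section 3 is feasibility, acceptability and preliminary efficacy, and no decision rule rests on the arm difference. Nothing in the documents ranks literacy above the other covariates, so its choice rests on the content of the scale. That limits the weight of the point and is a reason to keep the t-test in the report.

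Finally, the enrolment survey described in Section 4 does not list the literacy scale, although the SAP says it is assessed at baseline. Some participants may lack a score, and a complete-case model could then lose more than one degree of freedom. The fix has to deal with this.

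What survives is the asymmetry: about 1% of interval width at risk, against about 12% gained at r = 0.5, using a variable the SAP says is collected.

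**Conclusion.** The point holds as an optional improvement. The planned t-tests are valid and may stand; they simply leave a content-relevant baseline covariate unused. The benefit rests on an assumed correlation: negligible near 0.15, modest at 0.3 and material only towards 0.5. The added protection is against a shift in the single allocation the trial will have, and against choosing a covariate after an imbalance has been seen. Even at r = 0.5 the detectable difference is about 0.71 SD, so adjustment does not turn the pilot into a well-powered comparison of the arms. The figures assume 25 analysed per arm and approximately normal variables, whereas the actual scores are short Likert scales. With 20 per arm, break-even moves only to about 0.17.

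**What to change.** Before the 24-week data are analysed, add to the Analysis Plan that each of FIM, AIM and IAM will also be analysed by a linear model with arm and baseline Digital Health Care Literacy score as the only terms. Report the adjusted mean difference (PEERNaija+ minus PEERNaija) with its 95% CI alongside the planned two-sample t-test. State that participants with a score at 24 weeks but no baseline literacy value stay in the model, for example by imputing the overall baseline mean of the covariate. Confirm that the scale is part of the enrolment assessment, since the Section 4 list omits it.

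The cost is a sentence or two in the SAP, one residual degree of freedom (48 to 47), and about 1% of interval width if literacy turns out to be unrelated to the scores. If the scale is administered at baseline as the SAP says, no new data are needed.

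### Sections 3, 4 and 6 do not agree on the efficacy outcome, and the SAP runs at least six within-arm tests at .05 with no lead outcome, time point or success rule

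*Combined protocol and SAP*

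**What the plan says.** Efficacy is described in three places.

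- **Section 3 (hypothesis).** The app "will be feasible, acceptable, and show preliminary efficacy in improving ART adherence".
- **Section 4 (Study Outcomes).** The app is expected to "show preliminary efficacy in improving HIV virologic control".
- **Section 6 (SAP, Secondary Outcomes).** "Secondary outcome is preliminary efficacy on viral load". The next sentence assesses that outcome by "comparing change in HIV viral load (from baseline to 24 weeks), and self-reported adherence from baseline to 12 weeks, and baseline to 24 weeks".

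The SAP's Analysis Plan then calls for "pre-post comparison of adherence measures at baseline, 12, and at 24 weeks, and pre-post comparison of viral load measures at baseline and 24 weeks", for both study groups. The method is described as "using paired tests (e.g., paired t-tests, signed rank tests, or McNemar's tests, as appropriate"), and the threshold for every one of these tests is stated once: "with a significance level set at $p \leq .05$ (2-tailed test"). The two groups are the social-incentive arm and the social-plus-financial arm, 25 participants each (Section 4).

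Neither the protocol nor the SAP ranks these outcomes, picks one time point or one adherence measure, adjusts for the number of tests, labels the paired tests as exploratory, or says what result would count as preliminary efficacy. The only analyses introduced as exploring associations are the univariate regressions at the end of the SAP.

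**The concern.** Adherence and viral load are not interchangeable. Section 2 reports that 26% of young patients with a medication possession ratio above 94% still had virologic failure. The study could therefore show a change on one outcome and none on the other, and the documents do not say what would then be concluded.

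Because the SAP sets a formal significance threshold, its p-values will be read as tests of the hypothesis. With two versions of that hypothesis and several tests per arm, the choice of what to call efficacy can be made after the results are known. Section 7 says the project will be the basis for a larger intervention trial. A result picked for its significance could carry the wrong outcome, or an inflated effect, into that trial's design.

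**Working it through.** The documents give no power, effect size or familywise error rate, so there is no stated figure to reproduce.

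**1. Count the tests.** From the SAP's Secondary Outcomes and Analysis Plan, each arm has three contrasts: adherence 0–12 weeks, adherence 0–24 weeks, and viral load 0–24 weeks. Two arms give 3 × 2 = 6 paired tests.

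Six is a minimum, because it assumes one adherence measure:

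- The Analysis Plan refers to adherence measures in the plural, and Section 4 lists four (app score, visual analogue scale, medication possession ratio, ACTG questionnaire).
- The SAP adds a chi-square test on whether the app helped participants miss fewer doses, also labelled preliminary efficacy.
- Section 4 includes viral load at 12 weeks; the SAP does not.

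**2. Independent tests, no true change.**

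- Significant in either direction: 1 − 0.95^6 = 26.5%.
- Significant in the favourable direction, where each two-sided test allots .025: 1 − 0.975^6 = 14.1%.

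**3. Correlated tests.** The documents give no correlations, so these are assumed. Take a common correlation ρ among the three tests in an arm, independence between arms, normal test statistics, and c = 1.96. The chance that an arm has no significant test is

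P = ∫ φ(z) [Φ((c − √ρ z)/√(1−ρ)) − Φ((−c − √ρ z)/√(1−ρ))]³ dz.

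For the favourable direction only, drop the second Φ term. For two arms the result is 1 − P².

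| ρ | Either direction: one arm (1 − P) | Either direction: both arms | Favourable only: one arm | Favourable only: both arms |
|---|---|---|---|---|
| 0 | 14.263% | 26.5% | 7.314% | 14.1% |
| 0.3 | 13.624% | 25.4% | 6.832% | 13.2% |
| 0.5 | 12.544% | 23.5% | 6.274% | 12.2% |
| 0.7 | 10.921% | 20.6% | 5.461% | 10.6% |

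Simulated paired t-tests with 25 per arm and unequal correlations (0.5 to 0.8 between the two adherence changes, 0 to 0.7 between adherence and viral load) gave similar ranges: about 20 to 26% in either direction and 11 to 13% favourable.

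**4. Benchmark.** One two-sided test at .05 gives a false favourable result 2.5% of the time. The multiple is 10.6/2.5 = 4.2 to 14.1/2.5 = 5.6.

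**5. Sensitivity to the count (independent tests, either direction).**

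- Arms pooled, three tests: 1 − 0.95^3 = 14.3%.
- Six plus the chi-square test, seven tests: 1 − 0.95^7 = 30.2%.
- Six plus 12-week viral load in each arm, eight tests: 1 − 0.95^8 = 33.7%.
- One outcome and one time point, still tested in each arm, two tests: 1 − 0.95^2 = 9.75%.

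**The case against.** **The documents never say that one significant test is enough.** A reader might infer that the plan lets any one of the six establish efficacy. No sentence says so, and Section 4 describes efficacy as assessed on viral load and adherence together. This objection stands. What can be said is that no rule prevents selective reporting.

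**The either-direction rate is the wrong one for an efficacy claim.** A reader might conclude that the false-positive rate of the claim is four to five times .05. Both hypotheses are about improvement, so a significant worsening could not be reported as efficacy. This also stands: the relevant figure is 11 to 14%, to be compared with .025.

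**The tests are uncontrolled pre-post comparisons.** Regression to the mean or a time trend can make them significant without any app effect. That matters more if participants are selected for poor adherence, as the eligibility list in Section 5 (A.1) requires and the list in Section 4 does not. It is correct that the calculated rates leave this out, and a single pre-specified pre-post test would share the problem.

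**Adherence and viral load are steps on one pathway, and efficacy is secondary in a 50-person pilot.** Section 7 does present virologic control as following from adherence, and the primary outcomes are feasibility, acceptability and appropriateness. A reader might infer that strict familywise control is needed; for a secondary outcome in a pilot it is not. Splitting .05 over six tests (.0083 each) would raise the paired standardised change detectable with 25 per arm and 80% power from about 0.58 to about 0.75. None of this settles which outcome leads. The SAP names viral load and then includes adherence in its assessment.

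**Conclusion.** The inconsistency is explicit in the text: adherence in Section 3, virologic control in Section 4, and viral load assessed together with adherence in Section 6. The plan supplies at least six tests at two-sided .05 and no rule for reading them together.

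If nothing truly changes, at least one favourable significant result is expected in about 11 to 14% of such studies, against 2.5% for one two-sided test; in either direction, about 21 to 26%. These figures assume six tests, one adherence measure, independence between arms, and within-arm correlations from 0 to 0.7. They describe chance alone and are not the full error rate of an efficacy claim drawn from pre-post data.

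This bears on how the secondary results can be interpreted. It does not affect the primary outcomes.

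**What to change.** 1. State the same lead efficacy outcome and time point in Sections 3, 4 and 6. The SAP already points to change in viral load from baseline to 24 weeks. If the investigators prefer adherence, they should name one measure and one time point.
2. Name the single test that addresses it, and say whether it is a pooled pre-post test or a between-arm comparison. The SAP specifies neither for change in viral load. The choice matters: both arms receive the app, so a between-arm test addresses the added financial incentive, while a pooled pre-post test addresses change on the app without a control. Testing the lead outcome separately in each arm would leave two tests (9.75%).
3. Report all other adherence, time-point and arm-specific contrasts as exploratory estimates with 95% confidence intervals and no significance claim.

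No new data, visits or participants are needed. The cost is revised wording in three sections and a decision by the investigators on the lead outcome and comparison. The small downside is that a significant result on a supportive measure alone can no longer be reported as efficacy.
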